4.5 DOSE ESCALATION STOPPING RULES

The Medical Monitor will apply the following rules to determine if it is safe to proceed to the next Dose Level, or if dose escalation should stop. Pre-specified rules for pausing or stopping the whole study are described in Section 8.5 and rules for individual patient withdrawal are described in Section 8.4.

Should one of three patients in a Dose Level experience dose-limiting toxicity (DLT, see Section 8.1.2 for definition) within 7 days after receiving the first dose of the cells that is considered probably or definitely related to Descartes-30, 3 more patients will be enrolled and treated at that Dose Level. If only 1/6 of patients at that Dose Level has a DLT, and if the medical monitor agrees, treatment will proceed to the next higher Dose Level. If 2 or more out of 3 to 6 patients develop a DLT, no further patients will be dosed at that dose level. The MTD will be defined as the highest dose at which a maximum of 1 of 6 patients has a DLT. In Arm 2, up to 12 more patients who meet the eligibility criteria may be treated in each cohort (ARDS and PNA) at a dose up to MTD, provided that the medical monitor approves the enrollment of each such patient based on ongoing review of the cumulative safety data.

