- Urinalysis: Samples should be taken in the morning between 04:00 and 10:00 using the values closest to 10:00. (mandatory for Arm 1, only if done as part of standard of care at institution for Arm 2)
- ECG: Electrocardiogram may be performed as standard of care, at the discretion of the Investigator.
- Research blood collection: All protocol required research blood collection assessments must be conducted in accordance with Laboratory Manual.
- Chest Imaging: CT scan or Chest X-Ray (Once before first infusion and once between Days 1-6)
- AE review and evaluation
- PT/INR, PTT (mandatory for both Arms)

After completion of Descartes-30 infusion:

1. On Day(s) 0 and 2, Research Blood Collection at 30min (± 10 min). Please See Laboratory Manual for more details.
2. On Day(s) 0 and 2, PT/INR, PTT at 30min (± 10 min).
3. For details of post-infusion clinical monitoring for 4 hours (Arm 1) or 1 hour (Arm 2) after completing infusion, please see Section 7.1.2.3.

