7.1.2.3 POST-INFUSION OBSERVATION

There is a theoretical risk that MSCs can aggregate in pulmonary vasculature resulting in respiratory and hemodynamic instability. Thus, during and up to 4 hours (Arm 1) or 1 hour (Arm 2) following completion of infusion, the patient should be observed by a qualified study team staff to assess any dose-limiting infusion-related reactions, which are defined in Section 8.1.2. Patient's vital signs (i.e., core temperature, mean arterial pressure (mmHg), pulse (beats/min), respiratory rate (breaths/min), and transcutaneous oxygen saturation) should be monitored at least hourly (± 15 minutes or more frequently if clinically indicated). If applicable, changes in ventilation variables (i.e., type of ventilation (CPAP, BiPAP, or intubation), ventilation rate, pulse, tidal volume, positive end-expiratory pressure (PEEP)), vasoactive drugs and renal support will be recorded. These findings will be documented in the e-CRF.

Following the mandatory observation, the Investigator will decide if continuous monitoring can be discontinued. If the vital signs are not satisfactory and not stable for 4 hours (Arm 1) or 1 hour (Arm 2) post-infusion, vital signs will continue to be monitored at a minimum of every hour (± 15 minutes) or as clinically indicated until stable. If a reaction is suspected, the sequence of clinical events should be documented in detail into the e-CRF.

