8.2 RECORDING OF ADVERSE EVENTS

8.2.1 ADVERSE EVENT RECORDING

The adverse event recording period for this study starts after patient or legal representative signs consent and ends at Day 90 visit or when patient comes **off-study based on criteria in Section 8.4**. For SAE and SUSAR, reporting period starts with first Descartes-30 infusion and ends 7 days after last infusion. After 7 days, an AE (only in Arm 2), SAE (both Arms) or SUSAR (both Arms) is **only reported if it is probably or definitely attributed to Descartes-30 infusion**. At each contact with the subject during the adverse event recording period, the Investigator or his/her designee must seek information on adverse events by specific questioning and, as appropriate, by examination. Information on all adverse events should be recorded immediately in the source document, and in the appropriate adverse event module of the case report form (CRF). All clearly related signs, symptoms, and abnormal diagnostic procedures results should be recorded in the source document, though it should be grouped under one diagnosis.

All adverse events should be treated appropriately. If a concomitant medication or non-drug therapy is given, this action should be recorded on the Adverse Event CRF. Adverse events should be entered into the e-CRF system within 3 working days from the knowledge of the event took place. Once an adverse event is detected, it should be followed until its resolution or until it is judged to be permanent, and assessment should be made at each visit (or more frequently, if necessary) of any changes in severity, the suspected relationship to the study treatment, the interventions required to treat it, and the outcome.

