8.3 SAE AND SUSAR REPORTING

To ensure patient safety, every SAE and SUSAR, regardless of suspected causality, occurring during the adverse event reporting period defined in Section 8.2.1 must be reported to the Sponsor within 24 hours of learning of its occurrence. Recurrent episodes, complications, or progression of the initial SAE must be reported as follow-up information is received. An SAE occurring at a different time interval or otherwise considered completely unrelated to a previously reported one should be reported separately as a new event.

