8.5 STUDY PAUSING AND STOPPING RULES

Premature termination of the clinical trial may occur because of a regulatory authority decision, change in opinion of the IRB or Medical Monitor. Additionally, recruitment may be stopped for reasons of particularly low recruitment, protocol violations, or inadequate data recording. Specifically, study will be stopped if:

- Study Sponsor or a Regulatory Body decides for any reason that subject safety may be compromised by continuing the study.
- The Sponsor decides to discontinue the development of the intervention to be used in this study.

The study will be **paused if:**

- There is death that is reasonably attributed to study product before Day 4.
- Two subjects with Grade 3 or 4 adverse events to vital organs that are assessed as probably or definitely related to study product within the first 7 days after first infusion.

If the study is paused for the reasons above, the PI and members of the study team will meet in person or by teleconference within 24 hours of the event to have a thorough discussion of the event. Meeting minutes capturing the review of any ongoing investigations, including next steps in the management of the subject and any proposed changes to the protocol will be forwarded to the Medical Monitor. If all parties agree as to the event resolution, then the pause will be lifted. If the study is paused for manufacturing reasons, the Sponsor will make recommendations for process improvements to be implemented. Pending successful completion of a process validation run, the manufacturing pause will be lifted.

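### Arm 1 and Arm 2 safety data are collected under different stated rules, and the Section 9.2 safety tables take no account of it

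*Combined protocol and SAP*

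**What the plan says.** **Late AEs.** Section 8.2.1 runs AE recording from consent to the Day 90 visit, or until the patient comes off study, in both arms. It says: "Information on all adverse events should be recorded immediately in the source document, and in the appropriate adverse event module" of the CRF. For SAEs and SUSARs, the "reporting period starts with first Descartes-30 infusion and ends 7 days after last infusion". It then adds that "After 7 days, an AE (only in Arm 2), SAE (both Arms) or SUSAR (both Arms) is" reportable only on probable or definite attribution.

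**Infusion reactions.** Section 8.1.2 lists reactions that are DLTs if they occur within 4 hours of infusion, with no distinction by arm. Section 8.1.3 makes an infusion reaction an SAE. Section 7.1.2.3 gives the detection of those reactions as the purpose of observation and sets it "during and up to 4 hours (Arm 1) or 1 hour (Arm 2) following completion of infusion". Section 6.2 likewise refers to "post-infusion clinical monitoring for 4 hours (Arm 1) or 1 hour (Arm 2) after completing infusion".

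**Laboratory tests.** Footnote v of the Schedule of Activities and Sections 6.2 to 6.4 make CBC, serum chemistry and urinalysis mandatory in Arm 1 from Day 0 to Day 7. In Arm 2 they are done only where they are standard of care. CRP, ferritin, D-dimer, PT/INR and PTT are mandatory in both arms.

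**Analysis.** Section 3 makes the description of AEs, SAEs and clinical assessments the substance of the primary objective. The readable text of Section 9.2 says that AEs, laboratory tests and other safety parameters are tabulated descriptively. It names no time window, arm split or denominator.

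**The concern.** A count of events depends on how hard one looks and what one writes down. Here both differ by arm under stated rules. A lower number of late non-serious AEs, infusion reactions or laboratory abnormalities in Arm 2 could therefore reflect the collection rule and not the product. Arm 2 is up to 24 of about 36 patients, so a pooled rate would also be diluted if the rule suppresses events there.

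The tables matter because descriptive safety is the primary objective and Arm 2 exists to characterise risk and benefit further. Section 4.5 also makes each Arm 2 enrolment depend on the medical monitor's review of cumulative safety data.

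Two places also fail to fit together. Within Section 8.2.1, the instruction to record everything sits beside a limit on what is reported. And the 4 h reaction definition in Section 8.1.2 is paired with 1 h of mandated observation in Arm 2.

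**Working it through.** The plan gives no figure to reproduce on this point. The check sets the sections side by side and works out what the schedule implies.

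**1. Late non-serious AEs.** Inputs: infusions on Days 0, 1 and 2 (Synopsis); delay of up to 96 h = 4 days (Section 7.1.2.1); nominal end at Day 90 (Section 8.2.1). With S the last unfiltered day, the filtered time in Arm 2 is 90 − S.

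- Counted from last infusion, on schedule: S = 2 + 7 = 9; 90 − 9 = 81 days (81/90 = 90%).
- Counted from first infusion: S = 0 + 7 = 7; 90 − 7 = 83 days.
- Counted from last infusion, with infusions 2 and 3 each delayed 96 h (assuming the allowance applies per infusion): infusion 2 on Day 1 + 4 = 5; infusion 3 on Day 5 + 1 + 4 = 10; S = 10 + 7 = 17; 90 − 17 = 73 days.
- If the limit concerns only reporting to the sponsor and the CRF takes every AE: 0 days.

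In Arm 1 the figure is 0 throughout. The last-infusion anchor is the natural one, because the sentence just before counts that way. The other 7-day safety windows count from the first infusion ("within 7 days after receiving the first dose of the cells" in Section 4.5, "within the first 7 days after first infusion" in Section 8.5), but they serve escalation and pausing. Calendar days also exaggerate the gap: after Day 7 there are at most four scheduled contacts (Days 14, 21, 28 and 90), and Days 14 and 21 can be omitted after hospital discharge.

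**2. Infusion reactions.** Mandated observation over three infusions is 3 × 4 = 12 h in Arm 1 and 3 × 1 = 3 h, as a minimum, in Arm 2. Sections 6.2 and 7.1.2.3 count from completion of infusion; Section 8.1.2 gives no starting point.

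- If the 4 h reaction period starts at completion, Arm 2 observation covers 1/4 = 25% of it.
- If it starts with the infusion, which lasts 30-90 minutes (Section 6.2) and is itself observed, Arm 2 coverage is (0.5 + 1)/4 = 37.5% to (1.5 + 1)/4 = 62.5%.
- Arm 1 observation covers the whole period either way.

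**3. Laboratory tests.** Days on which CBC, chemistry and urinalysis are mandatory after screening, for a patient dosed on schedule and in the administering unit through Day 7: Arm 1, 3 (Days 0-2) + 4 (Days 3-6) + 1 (Day 7) = 8; Arm 2, 0. On Days 14 to 28, CBC and chemistry are standard of care in both arms (Section 6.5). Under Section 8.1.1 an abnormal value becomes an AE only if it has a clinical consequence or the investigator considers it of significant clinical impact, so some but not all of this difference can pass into AE counts.

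**4. Analysis text.** Nothing in the readable text of Section 9.2 restricts AEs to a period collected alike in both arms, or asks for the number of patients tested.

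**The case against.** The best defence is that lighter collection in an expansion arm is a deliberate choice. Section 9.1 says the objectives are not inferential, and no pooled or between-arm table is planned. Arm is also confounded with dose and, for the PNA cohort, with indication, so a side-by-side count would be hard to read even with uniform collection. All of that stands. It lowers the weight of the point but does not answer it: descriptive tables will be produced, and a reader needs to know what each count could have captured.

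A reader might infer more than the documents support:

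- *Late Arm 2 AEs are lost.* This is not established. Questioning at every contact and CRF entry of all AEs are required without regard to arm. Only the reporting sentence differs.
- *Reactions after the first hour in Arm 2 go unseen.* This is not supported. Section 7.1.2.3 requires at least hourly vital signs to continue until an unstable patient is stable; that is a rule and not an option. The reactions in Section 8.1.2 are major inpatient events, and vasoactive drugs and ventilation settings are recorded daily for ICU patients through Day 7. That daily recording does not extend to patients outside the ICU, which the PNA cohort allows.
- *SAE reporting differs by arm or contradicts itself.* It does neither. The late-SAE filter is the same in both arms. Section 8.3 requires that "every SAE and SUSAR, regardless of suspected causality, occurring during the adverse event reporting period defined in Section 8.2.1 must be reported", which agrees with Section 8.2.1 once the SAE reporting period is the one meant.
- *The MTD or mortality is biased.* The MTD is set in Arm 1, and Day 28 all-cause mortality does not depend on these rules.

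**Conclusion.** The point holds as a matter of collection rules and table design. The differences in mandated observation (4 h against 1 h per infusion) and in mandatory CBC, chemistry and urinalysis (8 days against 0) are explicit, and confidence in them is high. These figures measure what is mandated, not what will be done or detected.

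The late-AE difference is conditional. It is about 81 of 90 days if the reporting limit governs the CRF and the period runs from the last infusion on schedule, 73 to 83 days under the other delay and anchor assumptions, and 0 if the limit concerns sponsor reporting only. Confidence there is medium.

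The documents give no event rates, so the effect on counts is unknown and none is projected. The weight lies between a minor point and one that should be fixed: it touches the primary descriptive safety output and is cheap to repair, but it threatens neither the primary endpoint nor any planned comparison.

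**What to change.** 1. **Section 8.2.1.** Say whether a late, unattributed, non-serious AE in Arm 2 is entered in the CRF, so that the recording and reporting sentences agree. State whether the 7 days run from first or last infusion.
2. **Section 9.2, AE tables.** Limit any pooled or side-by-side AE table to all-cause events from first infusion to the end of the period that is unfiltered in both arms: 7 days after last infusion, or Day 7 if the sponsor anchors at first infusion. Tabulate later events separately by arm and cohort, with the collection rule in a footnote.
3. **Section 9.2, reactions and laboratory tables.** List reactions meeting Section 8.1.2 with onset time and whether onset fell inside mandated observation. Give the number tested by arm and visit in laboratory tables.
4. **Sections 6.2, 7.1.2.3 and 8.1.2.** Reconcile the observation period with the reaction period, including when each starts. No observation time is proposed here.

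Section 8.3 needs no change. Items 2 and 3 disclose the differences in observation and laboratory testing; they do not remove them. The cost is wording, footnotes and denominators, with no extra visits, samples or patients. Depending on how the sponsor settles items 1 and 4, Arm 2 CRF entry or staff observation could increase.

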4.4 DOSE ESCALATION RULES

A minimum of three patients will be dosed at each dose level. In the dose escalation arm, there will be a minimum of 7 days between each patient's first cell infusion. At the time a patient is diagnosed with ARDS, the clinic will contact the sponsor who, by default, will assign the patient to the next slot in the active dose level. Patients will receive three doses of Descartes-30 cells on Days 0,1 and 2. On Day 7 or last day in ICU, whichever comes earlier, the Principal Investigator will review the clinical data with the Medical Monitor and authorize the next patient's infusion if there is no safety concern. The selection of Day 7 for safety review is based upon preclinical data demonstrating that Dnase expression wanes over 7 days. Furthermore, the study will not proceed to the next dose level until: 1) at least 3 patients in the previous dose level have been observed through Primary Safety Review; 2) no study stopping rules have been triggered; and 3) the medical safety monitor has reviewed the cumulative safety data and concluded and documented that the next Dose Level may be initiated.

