6.6 LONG-TERM FOLLOW-UP (DAY 90± 14)

On Day 90± 14 days, an in-person visit, or telemedicine will be arranged to complete the assessments listed below. If any of the laboratory assessments cannot be performed due to inability to arrange a blood collection, it will not be considered as protocol deviation.

- Physical Exams: Abbreviated, targeted physical examinations (i.e., assessments of the skin, respiratory, cardiovascular system, and abdomen [liver and spleen]), will be performed at time points specified in the Schedule of Activities (Section 1) and will be based on the subject's clinical status and what the clinic staff deem is appropriate.
- Concomitant medications
- Clinical End-point Assessment includes: Survival (Y/N), On mechanical ventilation (Y/N), In ICU (Y/N), In Hospital (Y/N), Use of anti-coagulation (drug, dose, intent: prophylaxis vs therapeutic), WHO Ordinal Score (See Appendix D for scale). If patient is in ICU then the following assessment will be completed: Sequential Organ Failure Assessment (SOFA), PaO₂/FiO₂, following ventilation parameters (as applicable): type of ventilation (CPAP, BiPAP, or intubation)/ ventilation rate/ pulse/ tidal volume/ positive end-expiratory pressure (PEEP), recording of vasoactive drugs and renal support, recording of supportive interventions that can impact clinical endpoints (use of prone ventilation, use of paralytics, use of pulmonary vasodilators, use of corticosteroids, use of oral decontamination and raising the head of the patient at least 30° to prevent ventilator-associated pneumonia)
- Vital Signs: include core temperature, mean arterial pressure (mmHg), pulse (beats/min), respiratory rate (breaths/min).
- Research blood collection: Can be omitted if visit is telemedicine. All protocol required research blood collection assessments must be conducted in accordance with Laboratory Manual
- AE review and evaluation

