7.1.2 DOSING AND ADMINISTRATION

7.1.2.1 PRE-INFUSION MONITORING AND DELAY OF CELL INFUSION

[figure not shown]
Infusions can be delayed up to 96 hours based on PI discretion. Prior to all Descartes-30 infusions, patients should be observed for 2 hours (\pm 30 min) to document their stability by meeting the following parameters and based on PI's best clinical judgement:

1. Patient is not requiring a change in ventilator settings
2. Stable use of vasopressors if the patient required vasopressors for blood pressure support.
Stable use is defined as increasing no more than 50% of baseline recorded at initiation of monitoring.

During 2-hour monitoring, following parameters should be recorded at least every 30 min: ventilation variables [type of ventilation (CPAP, BiPAP, or intubation), ventilation rate, pulse, tidal volume, positive end-expiratory pressure (PEEP)], recording of vasoactive drugs and renal support and vital signs [include core temperature, mean arterial pressure (mmHg), pulse (beats/min), respiratory rate (breaths/min)]. If patients do not meet stability criteria for 2 hours, infusion can be delayed for up to 96 hours. If infusion is delayed, the patient will be periodically monitored to assess stability. If infusion is delayed more than 96 hours due to medical instability, patients will come off study treatment. Infusions can also be delayed up to 96 hours in case of a holiday or by PI's discretion.

Patients experiencing toxicities that are probably or definitely related to Descartes-30 will have their next Descartes-30 dose delayed until these toxicities have resolved to at least Grade 2, unless in the documented opinion of the site Principal Investigator and the medical monitor it is reasonable to proceed. During this period, patients will be assessed to record adverse events and decide whether the patient meets criteria for cell infusion. The discussions between the Medical Monitor and site Principal Investigator will be documented. If a dose is delayed for more than 96 hours, the patient will come off study treatment.

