8.3.3 FDA NOTIFICATION

The Sponsor is required to report certain study events in an expedited fashion to the FDA. These written notifications of adverse events are referred to as IND safety reports. The sponsor must report an IND safety reports as described in:

<http://www.fda.gov/downloads/Drugs/GuidanceComplianceRegulatoryInformation/Guidances/UCM227351.pdf>

The following describes the safety reporting requirements by timeline for reporting and associated type of event:

- **within 7 Calendar Days** any study event that is unexpected, fatal or life-threatening suspected adverse reaction; or
- **within 15 Calendar Days** any study event that is unexpected, suspected adverse reaction that is serious, but not fatal or life-threatening -or- a previous adverse event that was not initially deemed reportable but is later found to fit the criteria for reporting, any finding from tests in laboratory animals that suggest a significant risk for human subjects including reports of mutagenicity, teratogenicity, or carcinogenicity or reports of significant organ toxicity at or near the expected human exposure.

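### From 7 days after the last infusion, Section 8.2.1 sets a higher causality bar for site SAE reports than the suspected-reaction trigger in Section 8.3.3, which leaves a gap in 24-hour notification of the sponsor

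*Combined protocol and SAP*

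**What the plan says.** Four sections govern how a serious event travels from the site to the sponsor and on to the FDA.

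- **Section 8.2.1** starts AE recording at consent; it "ends at Day 90 visit or when patient comes" off study. For SAEs and SUSARs the "reporting period starts with first Descartes-30 infusion and ends 7 days after last infusion". Beyond that point an SAE or SUSAR (both arms) or an AE (Arm 2 only) is "only reported if it is probably or definitely attributed to Descartes-30 infusion".
- **Section 8.3** requires 24-hour reporting to the sponsor of "every SAE and SUSAR, regardless of suspected causality", but the same sentence confines this to the period that 8.2.1 defines.
- **Section 8.3.1** asks for SAEs and SUSARs to reach the sponsor by fax within 24 hours and states no period at all.
- **Section 8.3.3** gives the sponsor 7 calendar days for "any study event that is unexpected, fatal or life-threatening suspected adverse reaction", and 15 days for unexpected suspected reactions that are serious but not fatal or life-threatening. It states neither a time limit after dosing nor a probable-or-definite threshold.

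**The concern.** The site's duty to report and the sponsor's duty to report rest on different causality standards. Suspicion is enough to trigger a sponsor report. In the late period, suspicion alone does not oblige the site to tell the sponsor within 24 hours. The sponsor's clock can run only on events it knows about, so a site that follows 8.2.1 to the letter may leave the sponsor unaware of an event that 8.3.3 obliges it to send.

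Safety is the primary objective, and the synopsis says it is judged principally on AEs and SAEs. Late events also bear on decisions taken while the trial runs. Section 4.4 requires a review of cumulative safety data before each escalation, and Section 4.5 requires the medical monitor to approve each Arm 2 patient on such data. First infusions in Arm 1 are at least 7 days apart. When the third patient at a dose level starts, the first is therefore at Day 14 or later (2 × 7), already in the restricted period.

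**Working it through.** **Step 1. Is there a gap?** Take an SAE that begins after the window closes, is unexpected, and is suspected to be due to the product but rated below probable.

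- 8.2.1: outside the reporting period and below the bar, so no report is due.
- 8.3: applies only inside the 8.2.1 period, so it adds nothing.
- 8.3.1: read on its own, a 24-hour report is due, which contradicts 8.2.1.
- 8.3.3: the event meets the 7-day or 15-day trigger.

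If 8.2.1 governs, the 24-hour route is closed for an event that the sponsor must send on. If 8.3.1 governs, 8.2.1 is wrong. The text needs repair on either reading.

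**Step 2. How long does it last?** The plan gives no figure to reproduce. The inputs are:

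- Planned last infusion, Day 2: "Patients will receive three doses of Descartes-30 cells on Days 0,1 and 2" (Section 4.4).
- Window: last infusion plus 7 days (Section 8.2.1).
- Permitted delay, 96 hours (4 days): "Infusions can be delayed up to 96 hours based on PI discretion" (Section 7.1.2.1). Delaying only the third infusion moves the last one to Day 6. Delaying the second and then the third by 96 hours each moves it to Day 10.
- Final visit, Day 76 to Day 104: "On Day 90± 14 days, an in-person visit, or telemedicine will be arranged" (Section 6.6).

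Restricted share = (final day − (last infusion day + 7)) / final day.

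| Last infusion | Window closes | Final visit Day 76 | Final visit Day 90 | Final visit Day 104 |
|---|---|---|---|---|
| Day 2 | Day 9 | 67/76 = 88.2% | 81/90 = 90.0% | 95/104 = 91.3% |
| Day 6 | Day 13 | 63/76 = 82.9% | 77/90 = 85.6% | 91/104 = 87.5% |
| Day 10 | Day 17 | 59/76 = 77.6% | 73/90 = 81.1% | 87/104 = 83.7% |

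The planned value is 90.0% and the range is 77.6% to 91.3%. The table assumes that all three infusions are given and that the patient is followed to the final visit.

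**Step 3. What still reaches the sponsor by other routes?**

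- AEs are recorded to the Day 90 visit and entered in the e-CRF within 3 working days (8.2.1). The late limit on AEs names Arm 2 only, so a late Arm 1 SAE should still appear as an AE entry.
- In Arm 2, 8.2.1 asks for all AEs to be recorded and also limits which late ones are reported. The text does not settle what is captured.
- Survival is collected at Days 14, 21, 28 and 90 (Sections 1, 6.5 and 6.6; the Day 14 and 21 visits may be omitted after discharge), and deaths go to the IRB (8.3.2).

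None of these is the 24-hour report with a narrative and an investigator's causality assessment that 8.3.1 describes.

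**The case against.** The best defense is that the higher bar is deliberate. Background SAEs are frequent in ventilated patients. Section 7.2.2 expects toxicity within hours of infusion, and Section 4.4 ties the 7-day safety review to waning DNase expression. The same probable-or-definite wording appears in the delay rule (7.1.2.1), the escalation rule (4.5), the attribution-based part of the DLT definition (8.1.2) and one of the pausing rules (8.5). This is a fair reason to limit late reports. It does not explain a bar above the one in 8.3.3, which the sponsor must meet whatever the site's threshold. Section 7.2.2 itself calls the absence of toxicity from the DNases a hypothesis to be tested.

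The defense is right that several stronger readings fail:

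- *Late SAEs are lost, so the sponsor cannot judge causality.* Not shown. AE entries continue, Section 8.1.3 lets the sponsor judge seriousness, and Section 10.3 has the medical monitor review safety information across sites. What is lost is the 24-hour route.
- *The mortality result is filtered.* It is not. Survival status is collected whatever the attribution.
- *The MTD is biased.* It is not. Section 4.5 counts DLTs within 7 days of the first dose, before the window closes.
- *Late thromboembolism is the obvious missed event.* Section 7.2.2.3 directs attention to the first 24 hours after infusion, so it does not support that example.
- *Some number of reactions will go unreported.* The documents give no late SAE rate and no split by attribution. Enrollment is variously about 36 (synopsis), 33 (4.2) and 21 (5), so no count can be defended.

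**Conclusion.** The point holds as an inconsistency in expedited safety reporting. For 81 of 90 calendar days on the planned schedule (range 77.6% to 91.3%), 8.2.1 does not require a 24-hour site report for an SAE that is suspected but rated below probable, although 8.3.3 may require the sponsor to report it and 8.3.1 seems to require the site to. The percentage is a share of calendar follow-up for a patient followed to the final visit. A reader might take it as a share of SAEs or of risk, and nothing in the documents supports that.

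The conclusion assumes that *suspected* covers a lower degree of causality than *probable*. The documents define no causality scale, do not define *suspected*, and have no category of possible relationship; Section 8.5 adds a further wording for deaths (reasonably attributed). The missing definition is part of the problem. The primary endpoint and the planned mortality summary stand as they are.

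**What to change.** Amend 8.2.1, 8.3, 8.3.1 and 8.3.3 together so that one causality standard and one period govern SAE reporting to the sponsor:

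- Define *suspected adverse reaction* once and use that term in all four sections.
- After 7 days from the last infusion and through Day 90, require a 24-hour report to the sponsor of every SAE that is a suspected adverse reaction, and of every death whatever its attribution.
- State in 8.2.1 whether late Arm 2 AEs below the bar are still recorded in the e-CRF.

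The cost is a short amendment and a small number of extra SAE forms, in a population where serious events are common. Late SAEs that are not suspected, other than deaths, would stay outside the 24-hour route, so the sponsor is not flooded with background ICU events. Treatment, visits and analyses do not change.
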